5.6.2 Information Collected at Pediatric Follow-up

Infant at outcome

- Date of follow-up evaluation
- Current age of infant (at the time of assessment)
- Gender
- Gestational age at birth
- APGAR scores at birth
- Birth weight, length, head circumference and corresponding population-based percentiles
- Birth defect(s) and details, if noted
 - Type of birth defect(s)
 - Attribution to Savella drug therapy
 - Other factors that might have contributed to the outcome
 - Defect absent/present on pre- or post-natal test
- Chromosomal abnormalities and details, if noted
- Immediate post-natal health problems requiring resuscitation, admission to the neonatal intensive care unit (NICU)
- Medications
- Surgical interventions required of pre-term infants
- Other serious infant adverse outcomes noted on physical examination
 - Evidence of alterations in fetal/infant growth (e.g., intrauterine growth restricted, small for gestational age, etc.)
 - Presence of functional deficit (e.g., poor muscle tone, abnormal reflexes)
 - Presence of biochemical abnormality
 - Presence of transient or infectious conditions
 - Symptoms of poor neonatal adaptation (i.e., neonatal withdrawal)
 - Persistent pulmonary hypertension of the newborn

Infant at 4 and 12 months

- Date of follow-up evaluation
- Current age of infant (at the time of assessment)
- Birth weight, length, head circumference and corresponding population-based percentiles
- Birth defect(s) detected since last assessment and details, if noted
 - Type of birth defect(s)
 - Attribution to Savella drug therapy
 - Other factors that might have contributed to the outcome
 - Defect absent/present on pre- or post-natal test
- Chromosomal abnormalities and details, if noted
- Medications
 - Other serious infant adverse outcomes noted on physical examination

- Evidence of alterations in infant growth
- Presence of functional deficits
- Developmental delays

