6.2.3 Evaluable Registry Reports

An evaluable report is a case, submitted or verified by a HCP, containing at least the minimum criteria for Registry enrollment, and is not lost to follow-up. Prospectively reported evaluable cases with known outcomes are included in the primary analyses for the Interim Report produced annually and the Final Report. Retrospective reports are summarized separately in the Interim Reports and the Final Report.

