- Conditions that are attributed to prematurity alone, such as patent ductus arteriosus (PDA), patent foramen ovale (PFO), and inguinal hernias. If these conditions are present in infants born < 37 weeks gestational age or if gestational age is unavailable, weighing < 2500 grams, they are not considered birth defects. If these conditions are present in infants born ≥ 37 weeks gestational age, they are considered birth defects.
- Infants with only transient or infectious conditions, or biochemical abnormalities, are classified as being without birth defects unless there is a possibility that the condition reflects an unrecognized birth defect.

The Registry focuses on birth defect data detected and reported during pregnancy and up to one year of age for live born infants. Most major structural defects and clusters of minor abnormalities are readily apparent during this time frame. However, under ascertainment of birth defects is possible. The Registry does update case reports if information is received on any birth defect diagnosed with signs/symptoms occurring up to six years of age. However, this information is not systematically collected. The Registry collects information on minor abnormalities, transient or infectious conditions, and biochemical abnormalities that reporting clinicians deem important.

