8.5 Data Analysis

8.5.1 Birth Defects

For the primary analysis, the prevalence of birth defects reported to the Registry in the evaluable population is calculated by dividing the number of birth defects (i.e., the number of pregnancy outcomes occurring at or after 20 weeks gestation with a noted birth defect) by the total number of live births in the evaluable population. Pregnancy losses with reported birth defects occurring at or after 20 weeks gestation are included in the numerator of the estimate of risk for birth defects to increase sensitivity and to allow for comparison with the MACDP which calculates rates using this convention. A secondary analysis is conducted including pregnancy losses with reported birth defects occurring at any gestational age in the calculation of risk. An additional secondary analysis will be performed that only includes birth defects that are noted from ultrasound examinations (pre-natal or post-natal). Birth defects will be reported by outcome (live birth (overall and full-term or pre-term)), stillbirth, induced abortion (elective or therapeutic) and trimester of exposure. All defects detected <20 weeks of gestation will be described in the report. Additionally, birth defects noted by non-HCP reports will be reported descriptively.

Calculations of 95% confidence intervals (two-sided) for individual birth defect rates are based on the exact method using binomial probability distribution. The prevalence in exposed cases is compared with the observed prevalence in the MACDP (Correa et al., 2007). In addition, one-sample binomial tests at the two-sided 0.05 level are used to test the association of elevated levels of major birth defects in pregnancy exposures to Savella by comparing the observed proportion of birth defects in the Registry with rates from the MACDP.

Enrolled pregnancies that are LTFU without pregnancy outcome, as defined in section 6.2.6, will be enumerated in the interim/final report, but will not be included in the

calculation of risk. Prospectively enrolled pregnancies with an outcome will be included in the calculation of risk regardless of whether they are subsequently designated as infant LTFU.

If feasible, comparisons between the Registry and an appropriate external comparison group will be examined.

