9.1 Regulatory Agency Reporting Considerations

The Registry follows the FDA Guidance for Industry, *Establishing Pregnancy Exposure Registries* (FDA, 2002) for regulatory reporting of adverse events to FDA. "The Agency considers pregnancy exposure registry reports (both prospective and retrospective) as derived from active solicitation of patient information." Therefore Allergan is responsible for, "reporting any serious and unexpected events by regulatory definition and where a reasonable possibility exists that the drug or biological product caused the adverse event within 15 calendar-days" (FDA, 2002).

For FDA status reporting, the Registry Interim Report can be appended to the annual report submission as described in the FDA Guidance (FDA, 2002). The Interim Report, published annually, contains the background, Registry design, and analysis plan. It summarizes the status and the cumulative data on the Registry to date. In addition, the Registry can generate individual case line listings to assist Allergan in preparation of its submission. The Interim Report, generated annually, is cumulative and current to the most recent data cutoff period.

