Birth Defect – A "birth defect" in this Registry follows the CDC guidelines and is defined as (1) any major structural malformation or chromosomal defect diagnosed or with signs/symptoms before one year of age, (2) on a case-by-case basis, subject to independent review, any cluster of at least two minor abnormalities (cases with two minor defects will trigger further investigation by the registry's birth defect evaluator; the determination of the birth defect evaluator would then decide whether the specifics of any particular case merit its inclusion as a birth defect case. Cases with three or more minor defects will be counted as a birth defect cases., or (3) on a case-by-case basis, subject to independent review, any structural or chromosomal defect detected in the prenatal evaluation of a pregnancy or in the gross or pathologic examination of an abortus, fetus, or deceased infant. The Registry excludes birth defects attributed to prematurity itself (e.g., patent ductus arteriosus, patent foramen ovale, and inguinal hernias).

Corrected EDD – Estimated date of delivery obtained by prenatal test (e.g., ultrasound)

Ectopic pregnancy – Implantation of a conception outside of the uterus.

- **Induced abortion** Voluntary interruption of pregnancy. Includes pregnancy termination which occurs electively or therapeutically, to preserve maternal health, or due to fetal abnormalities.
- MACDP (The Metropolitan Atlanta Congenital Defects Program) A program that monitors all major birth defects in five counties of the metropolitan Atlanta area (Clayton, Cobb, DeKalb, Fulton, and Gwinnett) with approximately 50,000 annual births from a population of about 2.9 million. MACDP acts as the model for many state-based programs and as a resource for the development of uniform methods and approaches to birth defect surveillance.

Maternal/fetal death – A pregnant woman expires with the fetus in utero.

Molar pregnancy – A conception that results in a gestational trophoblastic tumor.

- **Neonatal death** An infant expired after a live birth.
- **Pregnancy Category A** Controlled studies show no risk: Adequate, well-controlled studies in pregnant women have failed to demonstrate risk to the fetus.

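### Annual interim prevalence counts infants under one year with no defect reported so far as defect-free, although defects are ascertained to 12 months; this component pushes the interim rate down

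*Protocol*

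**What the plan says.** **Entry to the analysis.** Protocol 6.2.3: "Prospectively reported evaluable cases with known outcomes are included in the primary analyses for the Interim Report produced annually and the Final Report". Section 8.5.1 divides the outcomes at or after 20 weeks that have a defect "by the total number of live births in the evaluable population". Neither section sets a minimum infant age or asks for completed pediatric follow-up.

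**Ascertainment window.** Section 7.1.2: "The Registry focuses on birth defect data detected and reported during pregnancy and up to one year of age for live born infants". The Glossary entry for a birth defect covers "any major structural malformation or chromosomal defect diagnosed or with signs/symptoms before one year of age". Section 5.6.1 schedules pediatric forms just after birth and at 4 and 12 months. According to 5.6.2, the two later forms record "Birth defect(s) detected since last assessment and details, if noted".

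**Timing and use.** Section 9.1: "The Interim Report, generated annually, is cumulative and current to the most recent data cutoff period". Section 8.5.1 gives the rate an exact 95% interval and a two-sided 5% one-sample binomial test against the MACDP rate, which section 8.3 sets at 2.78%.

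**Infants without follow-up.** Section 8.5.1: "Prospectively enrolled pregnancies with an outcome will be included in the calculation of risk regardless of whether they are subsequently designated as infant LTFU". Section 8.6 discusses bias from prenatal testing, voluntary reporting, pregnancies lost to follow-up, fetal losses and retrospective reports. It does not mention infants who are still under one year at the cut-off.

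**The concern.** An infant born a month before the cut-off is a full denominator unit, but its 4- and 12-month forms cannot yet exist. If its defect is already reported, it counts as a case. If not, it counts as a non-case, although most of the ascertainment window is still to come. The interim rate therefore mixes infants observed for a full year with infants observed for weeks.

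The Interim Report can accompany the annual submission to FDA (9.1), and the Scientific Advisory Committee reviews the accumulating data each year (7.3). For a registry meant to detect a signal, a component that lowers the rate works toward reassurance. Changes in the cumulative rate from one year to the next would also partly reflect the age mix at the cut-off.

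**Working it through.** **1. The plan's own figures (8.4).** Expected live births: 350 × 0.62 × 0.90 = 195.3, which is 196 rounded up. With n = 196 and a null rate of 2.78%, the smallest case count with an exact upper tail of at most 0.025 is 11: P(X ≥ 11 | 2.78%) = 0.0221, while P(X ≥ 10 | 2.78%) = 0.0487. Power is P(X ≥ 11 | 6.95%) = 0.807. The stated 80% is reproduced.

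**2. Direction.** Let a be the share of live births under one year at the cut-off, and s the share of one-year defects already reported for those infants. Then

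expected observed rate = true rate × [1 − a(1 − s)].

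The factor is below 1 whenever a > 0 and s < 1. The 4- and 12-month forms exist to record later-detected defects, so the plan itself allows for s < 1.

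**3. Assumptions for size.** The protocol gives neither the accrual rate nor the timing of detection. Assumed here:
- uniform accrual, enrollment at 12 weeks and birth at 39 weeks, so lag = (39 − 12)/52 = 0.519 year;
- a share f of one-year defects, 10% to 40%, is first recorded after the birth form, half by 4 months and half by 12 months;
- an infant under 4 months lacks all of f, and an infant aged 4 to 12 months lacks f/2.

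**4. Formulas.** With B = y − lag years of births at report year y (B of at least 1):
- share under 12 months = 1/B;
- share under 4 months = (1/3)/B;
- relative understatement = f × (1/3)/B + (f/2) × (2/3)/B = (2/3) × f/B.

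**5. Results.** The last column applies the understatement to a true rate of 2.78%.

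| Report year | B | Share under 12 months | Understatement, f = 10% | Understatement, f = 40% | Expected observed rate |
|---|---|---|---|---|---|
| 2 | 1.481 | 68% | 4.5% | 18% | 2.65% to 2.28% |
| 3 | 2.481 | 40% | 2.7% | 11% | 2.71% to 2.48% |
| 5 | 4.481 | 22% | 1.5% | 6.0% | 2.74% to 2.61% |
| 8 | 7.481 | 13% | 0.9% | 3.6% | 2.76% to 2.68% |

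In year 1, B = 0.481, so every live birth is under one year. Enrollment at 8 or 20 weeks moves the year-3 share only to 42% or 38%.

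**6. Against sampling error.** Five cases in 196 births (2.6%) have an exact 95% interval of 0.8% to 5.9%. The year-8 shortfall on 2.78% is about 0.02 to 0.10 percentage points, well inside that interval.

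**The case against.** The strongest reply is that this is a reporting lag. Each Interim Report is cumulative and replaces its predecessor (9.1, 13.1), so later-detected defects are added to the same infants. That largely stands. Each new report also brings in new births, however, so the component shrinks but does not vanish while enrollment continues.

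A second reply is that entry at pregnancy outcome was chosen deliberately, as the sentence in 8.5.1 on infants lost to follow-up shows. That sentence covers infants whose follow-up is never obtained. Infants not yet due for their contact are a different group, and no rule addresses them. The remark in 7.1.2 that defects may be under-ascertained is general.

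A third reply is that the early years may already be past: this version dates from September 2017, and section 6.1 mentions mailings in 2011. That is plausible, and the later rows of the table are then the relevant ones.

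Three stronger readings are tempting, but the protocol does not support them:
- **Lost power.** A reader might put a year-3 or year-5 age mix on 196 births and infer that the planned power is not reached. Section 8.4 claims no interim power, and nothing indicates that all 196 births would be analyzed with such a mix.
- **A rate biased low overall against 2.78%.** Section 7.1.2 says that counting clusters of minor defects may inflate the estimate. The comparator's age window is supported only indirectly, by the Glossary's statement that the definition follows CDC guidelines.
- **A truncated Final Report.** Section 14 does not tie the cut-off to the last 12-month contact, but that is silence. Section 1 has live-born infants followed to age one, and no passage permits an earlier cut-off.

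**Conclusion.** The point holds for the Interim Reports. Infants under one year with no defect reported so far are counted as defect-free in the annual prevalence, its exact interval and the MACDP test, and no passage corrects for this. The direction of this component follows from the text. Its size does not: the 2.7% to 11% (year 3), 1.5% to 6% (year 5) and roughly 1% to 4% (year 8) rest entirely on the assumed accrual pattern, enrollment week and share of defects recorded after the birth form. The effect is largest early, fades as reports are updated, and is small beside sampling error in later years. The net bias against 2.78% is unknown. The case for a change is that it is cheap and makes the interim figure interpretable.

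**What to change.** In 8.5.1:
- Keep the all-live-births rate, but label it provisional in Interim Reports.
- Beside it, report the prevalence, exact interval and MACDP comparison in the cohort whose 12-month date, plus the query window of section 6.3, precedes the cut-off. For losses at or after 20 weeks, use the expected delivery date plus 12 months, so that numerator and denominator cover the same cohort.
- Give the numbers of infants that have reached birth, 4 months and 12 months.

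State that the Final Report cut-off follows the last live-born infant's 12-month contact. Leave case-level signal review (7.3) unchanged, so that no defect report is delayed.

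**Cost.** Wording and one extra table from data already collected. The mature-cohort rate has a smaller denominator and a wider interval, and it leaves out recent births, including defects already known at birth. That is why it should stand beside the all-births rate and not replace it. The Final Report may come later. The fix removes only the part due to infants not yet old enough: infants lost to follow-up remain counted as non-cases, as 8.5.1 specifies.

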6.2.4 Patient Reports Not Confirmed by the Provider

Reports received directly from pregnant women that are not verified by the HCP are included in the Registry, but identified as a non-HCP-verified report. If the obstetric HCP does not provide the requested data after all follow-up attempts have been made by the Registry, the patient will be contacted to obtain interim and outcome information. Section 6.3 provides a complete description of the follow-up process. If she reports a live birth, the Registry requests her consent to contact the infant's HCP. These reports are analyzed separately and may be included in the analysis if appropriate.

6.2.5 Ineligible Registry Reports

A report that does not meet the eligibility criteria outlined in Section 4.1 is ineligible. Ineligible reports are not captured in the Registry database.

6.2.6 Invalid Registry Reports

An invalid case is a report for which the minimum criteria for Registry enrollment are never obtained despite requests for the missing data. If the minimum data are not provided on receipt of a prospective report, the case is considered pending until all attempts to resolve queries for missing data and requests for follow-up information are complete. If after all follow-up attempts, the minimum criteria are still not met, the case receives a status of "invalid" with a reason of "insufficient information". Section 6.3 provides a complete description of the follow-up process. Invalid reports are summarized for Allergan's safety reporting purposes, but are not included in the Registry analyses.

6.2.7 Losses to Follow-Up (LTFU)

A prospective report meeting the minimum criteria for enrollment but for which follow-up information on the pregnancy outcome (live birth, fetal loss, etc.) is never obtained, is unavailable, and/or where the indication of a birth defect is designated as "unknown" is considered "pregnancy lost to follow-up". For the infant portion of the Registry, live born infants where pediatric follow-up information is never obtained, is unavailable, and/or where infant status is designated as "unknown" is considered "infant lost to follow-up". Section 6.3 provides a complete description of the follow-up process. Losses to follow-up are tallied in the Registry Interim Reports and the Final Report, but are not included in the statistical analyses.

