8. STATISTICAL CONSIDERATIONS

8.1 Analysis Population

The primary population for analysis includes prospective evaluable cases that are not "lost to follow-up" (i.e., cases with appropriate outcome information and meeting the minimum criteria for evaluation). Retrospective cases are reviewed and reported separately.

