8.5.3 Adverse Pregnancy Outcomes

Overall and by-stratum point estimates of rates and 95% confidence intervals will be calculated for the following outcomes:

- Spontaneous abortions
- Stillbirths
- Induced abortions (overall and elective or therapeutic)
- Minor congenital anomalies,

Other adverse pregnancy outcomes among pregnancies exposed to Savella and their live births during the first year of life will be summarized as counts and percentages of the total number of prospective evaluable outcomes. Summaries will also be presented by subgroups including maternal age at conception (<25, 25-35, >35), family history of birth defects, smoking status, and alcohol use during pregnancy. Additional subgroups may be analyzed if deemed appropriate and necessary given the sample size. These other adverse pregnancy outcomes include:

- Functional deficits
- Alterations in fetal growth
- Transient or infectious conditions
- Biochemical abnormalities
- Pre-term infants with findings that persist and require surgical intervention

Strata are comprised by earliest trimester of exposure and potentially other variables as appropriate given the sample size, such as maternal age, history of birth defects, lifestyle variables, comorbidities, and concomitant drug exposures.

All chromosomal abnormalities, whether classified as a birth defect or other adverse outcome, will be displayed in a separate listing.

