8.6 Potential Biases

Because early prenatal testing is so prevalent in the US, it may be difficult to achieve adequate numbers of prospectively identified patients if all pregnancies with prior prenatal testing are excluded from the analysis. Therefore, the primary analyses includes pregnancies enrolled prior to outcome but after a prenatal test as long as the test does not indicate an abnormality. However, this practice could potentially bias the results by lowering the overall risk of birth defects (Honein et al., 1999). The analysis attempts to address whether this practice biases the results.

As reporting of pregnancies is totally voluntary, it is possible that even in prospectively reported cases, potential bias could exist. For example, high-risk pregnancies or low-risk pregnancies may be more likely to be reported.

Enrolled pregnancies that have reached their estimated date of delivery and for which outcome information is unobtainable are considered "lost to follow-up". It is possible that outcomes among pregnancies lost to follow-up could differ from those with documented outcomes. Because of differences in follow-up and reporting patterns, it is currently not possible to assess with any certainty what impact the potential biases the losses to follow-up may have on the analysis. However, efforts at comparing some of the characteristics of each group are conducted in an attempt to address this potential source of bias.

Following the MACDP convention, calculation of birth defect risk excludes fetal losses (spontaneous abortions, induced abortions, stillbirths, etc.) for which no birth defects have been detected as they may introduce a classification bias. It is unknown what percentage of these pregnancies consists of potentially normal outcomes or birth defects. The Registry attempts to obtain information on birth defects detected at the time of the outcome. However, the reporting physician may not know the condition of the aborted fetus.

While the Registry analysis is limited to prospective reports, some pregnancy exposures are reported following pregnancy outcome (retrospective cases). Each retrospective report is carefully reviewed. In general, retrospective reports of exposures to therapy following notification of outcome are biased toward reporting the severe and unusual

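### Section 6.2.7 counts known fetal losses with unknown defect status as lost to follow-up, which conflicts with 8.5.1 and 8.6 and can bias the secondary fetal-loss rates downward

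*Protocol*

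**What the plan says.** Protocol section 6.2.7 gives several routes to the status of pregnancy lost to follow-up, joined by an and/or. One is that the pregnancy outcome was never obtained or is unavailable. Another is a report "where the indication of a birth defect is designated as" unknown. Either is sufficient. The consequence is stated in the same section: "Losses to follow-up are tallied in the Registry Interim Reports and the Final Report, but are not included in the statistical analyses".

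Section 6.2.3 makes not being lost to follow-up part of the definition of an evaluable report, and section 8.1 restricts the primary analysis population in the same way. Section 8.5.3 then promises, for spontaneous abortions, stillbirths, induced abortions and minor anomalies: "Overall and by-stratum point estimates of rates and 95% confidence intervals will be calculated for the following outcomes". It names no separate population for these rates; its other adverse outcomes are percentages of the prospective evaluable outcomes.

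Two later sections describe loss to follow-up differently. Section 8.5.1 says: "Enrolled pregnancies that are LTFU without pregnancy outcome, as defined in section 6.2.6, will be enumerated in the interim/final report". It adds: "Prospectively enrolled pregnancies with an outcome will be included in the calculation of risk regardless of whether they are subsequently designated as infant LTFU". Section 8.6 describes a lost pregnancy as one past its estimated delivery date with no obtainable outcome information. Neither mentions defect status. Section 6.2.6, which 8.5.1 cites for the definition, covers invalid reports; the definition is in 6.2.7.

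On fetal losses, section 8.6 also acknowledges that "the reporting physician may not know the condition of the aborted fetus".

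**The concern.** A pregnancy that ended in a documented miscarriage is not lost to follow-up as far as the miscarriage rate is concerned. Removing it because nobody could say whether the fetus had a defect makes exclusion depend on the outcome being estimated. Live-born infants are to be assessed at birth, 4 and 12 months (section 5.6.1, subject to consent), so their defect status has several chances to be recorded. The glossary's spontaneous abortion category includes blighted ovum and missed and incomplete abortion, where a fetal examination is less likely.

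If the 6.2.7 wording is followed, the expected direction is fetal-loss rates too low and the live-birth share too high. These rates are the first secondary objective in section 2. In a safety registry, an understated loss rate errs on the reassuring side. The tally of losses to follow-up would also mix pregnancies nobody could trace with pregnancies whose outcome is on file.

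**Working it through.** **Plan figures.** Section 8.4 gives 350 enrolled pregnancies, 10% lost to follow-up and 62% of recognised pregnancies ending in live birth. Then 350 × 0.90 × 0.62 = 195.3 live births, against the stated 196, so the figure reproduces. The stated 80% power also reproduces: with n = 196, the exact binomial test rejects at 11 or more cases (upper tail 0.0221 at 2.78%), and power at 6.95% is 80.7%.

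**One case through the rules.** Take a prospective spontaneous abortion, outcome documented, defect status recorded as unknown.

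- 6.2.7: lost to follow-up, out of the statistical analyses.
- 6.2.3 and 8.1: not evaluable, out of the primary population.
- 8.5.1: it has an outcome, so it is not in the group excluded there as lost.
- 8.6: outcome information was obtained, so it is not lost; with no defect detected it is left out of the defect-risk calculation under a separate convention.
- 8.5.3: no population of its own for the rates, so it follows the evaluable population and the case leaves numerator and denominator.

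The same case is therefore lost under one definition and not under the other two.

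**Size under the 6.2.7 wording.** Followed pregnancies: 350 × 0.90 = 315, of which 195.3 are live births and 315 × 0.38 = 119.7 are not. Let u be the share of non-live outcomes with unknown defect status, and assume that no live birth has unknown status. The protocol gives no value for u.

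Apparent non-live share = 0.38(1 − u) / [0.62 + 0.38(1 − u)]

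| u (assumed) | Calculation | Apparent non-live share | Apparent live-birth share |
|---|---|---|---|
| 0% | 0.380 / 1.000 | 38.0% | 62.0% |
| 10% | 0.342 / 0.962 | 35.6% | 64.4% |
| 25% | 0.285 / 0.905 | 31.5% | 68.5% |
| 50% | 0.190 / 0.810 | 23.5% | 76.5% |
| 75% | 0.095 / 0.715 | 13.3% | 86.7% |
| 90% | 0.038 / 0.658 | 5.8% | 94.2% |

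**When there is no bias.** If 10% of live births also had unknown status, u = 10% gives 0.342 / (0.558 + 0.342) = 38.0%. The bias comes from the difference in unknown shares between losses and live births.

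**If the planned 10% already contains such cases.** Of 350 pregnancies, 0.38 × 350 = 133 are non-live. If all 35 planned losses to follow-up were among them, the apparent share is (133 − 35) / 315 = 31.1%.

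**Primary estimate.** Under 8.5.1 its denominator is live births, and its numerator is outcomes at or after 20 weeks with a noted defect. A fetal loss of unknown status is in neither.

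**The case against.** The best counter-argument is that the protocol handles unexamined losses elsewhere. Section 8.6 leaves fetal losses without a detected defect out of the defect-risk calculation and, in that context, remarks that the fetus's condition may be unknown. This suggests that such losses are thought of as no defect detected. The 6.2.7 clause requires the status to be designated unknown, the outcome item in 5.5.2 is whether a defect was noted, and nothing says how an unexamined loss is coded. This stands in part: how many losses the clause would remove depends on a coding choice that the document does not fix. It does not remove the conflict, because any loss that is coded unknown is excluded by 6.2.7. Nor does 8.5.1 settle the matter for 8.5.3, since its inclusion sentence concerns the defect-risk calculation.

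A reader might infer that these pregnancies vanish from every analysis. The documents do not support that. Losses to follow-up are still tallied, their baseline characteristics are compared with those of the evaluable population (8.5.2), and 8.5.1 and 8.6 point the other way. The tally and comparison make the exclusion visible but do not correct the rates.

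A reader might also infer that abortion rates will be grossly understated. Suppose 15% spontaneous abortion, 22% induced abortion and 1% stillbirth, with 20% of stillbirths of unknown status. The apparent spontaneous abortion rate is then 0.15(1 − u) / [0.62 + 0.37(1 − u) + 0.008], where u is the unknown share among abortions. That is 9.2%, 4.3% and 1.2% at u = 50%, 80% and 95%, but 14.0% and 12.4% at 10% and 25%. Neither the split nor u is in the protocol, so the extreme values cannot be presented as the expected result. The same applies to a loss tally of (35 + 315 × 0.37 × 0.8 + 315 × 0.01 × 0.2) / 350 = 37% at u = 80%. It assumes that the planned 10% counts missing outcomes only, while section 8.4 says just that the figure comes from similar registries.

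Finally, section 2 calls the registry primarily exploratory, and section 8.2 says its intervals are for estimation and not inference. That lowers the severity. It does not excuse a biased point estimate.

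**Conclusion.** The concern holds as a conflict of definitions with a possible bias in secondary estimates. Section 6.2.7, carried through 6.2.3 and 8.1, can remove known fetal losses from the 8.5.3 rates; 8.5.1 and 8.6 define loss to follow-up by missing outcome only. The bias is downward for fetal losses and upward for live births if unknown defect status is more frequent after losses. That is likely, but the protocol does not quantify it.

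On the protocol's 62% live-birth figure, and assuming no live birth has unknown status, the effect on the 38% non-live share runs from slight (35.6% at u = 10%) to severe (13.3% at u = 75%). The document does not show where in that range the registry would fall. The dropped fetal losses leave the primary prevalence, the planned power and the comparison with the 2.78% surveillance rate unchanged. Severity is moderate.

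**What to change.** 1. In 6.2.7, define pregnancy lost to follow-up as pregnancy outcome not obtained, in line with 8.5.1 and 8.6.
2. Add a separate status for outcome known, defect status unknown, and state that an unexamined fetal loss is coded there.
3. In 8.5.3, state that these pregnancies stay in numerator and denominator of all pregnancy-outcome rates and are excluded only from the defect calculation.
4. In 8.5.1, correct the cross-reference from 6.2.6 to 6.2.7.
5. Report the number in the new status by pregnancy outcome, so that the unknown share can be seen.

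The cost is a few sentences and one derived flag. Pregnancy outcome and birth defect noted are already separate items in 5.5.2, so no new data are needed.
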